6.7 Recruitment

It is recommended that during the development of this research protocol, the principal investigator requests the approval of the Research Ethics Committee and the Research Committee, as well as the authorization to the relevant regulatory entity, to publish or disseminate in the mass media, the invitation to participate in the study to those people who meet the eligibility criteria.

It is possible to discuss with other health professionals the opportunity for healthy subjects to be evaluated by an ophthalmologist at no cost, as well as cabinet exams that will allow the more accurate determination of their ocular clinical status by participating in a sponsored clinical research protocol. by Laboratorios Sophia, SA of C.V.

7. Methods Assignment of the intervention

7.1 Generation of the allocation sequence

The random numbers will be generated through the online tool:

www.randomization.com

Two strata corresponding to the intervention groups will be used, which will be balanced for a research center. The allocation will be 1: 1.

7.2 Blinding mechanism

Blinding will be performed by personnel assigned by the Clinical Operations Management of Laboratorios Sophia, S.A de C.V. Which will consist in the elimination of the primary label (commercial) in the case of Sophixín Ofteno® and the placement of a label identical to the other intervention. There will be a masking in the secondary packaging which will be identical for the interventions.

7.3 Implementation

The allocation sequence will be generated by personnel assigned by the Clinical Operations Management of Laboratorios Sophia, S.A de C.V. The research center will receive a set of envelopes which will contain the intervention number individually. The envelopes will be identical on the outside. Each of these envelopes will be shown to the participants for their election by the principal investigator or by a designated member of their team.

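### Section 7.3 offers outwardly identical envelopes for choice, so the order of the generated sequence does not govern assignment and the per-centre balance in 7.1 is not guaranteed

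*Combined protocol and SAP*

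**What the plan says.** On generation, section 7.1 takes the random numbers from an online tool and states: "Two strata corresponding to the intervention groups will be used, which will be balanced for a research center. The allocation will be 1: 1". It gives no block size, list length or number of lists.

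On implementation, section 7.3 has sponsor staff generate the sequence. It continues: "The research center will receive a set of envelopes which will contain the intervention number individually", and "The envelopes will be identical on the outside". The assignment step itself is: "Each of these envelopes will be shown to the participants for their election by the principal investigator or by a designated member of their team".

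No other section adds an order of use. The baseline-visit procedures (6.5.1.2) refer assignment back to section 7. Sections 7.2 and 7.4 cover masking: commercial labels are replaced and the bottles carry an assignment number. The protocol does not state whether envelopes are sealed, opaque or numbered outside, how many a centre receives, what the arm mix of a set is, or what happens to an envelope that is opened or passed over.

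**The concern.** A generated sequence works because each subject receives the next entry, fixed before anyone knew who that subject would be. Under 7.3 the subject's number depends on which of several indistinguishable envelopes is picked, so the list order has no role at the point of assignment. Three things follow.

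- Adherence to the sequence cannot be verified, because no entry is due to any particular subject.
- Any blocking built into the list is undone, so balance depends on the set being used up.
- The person presenting the envelopes could offer only some of them or allow a second pick, and 7.3 requires no record of either.

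Section 5.6.1 relies on randomisation together with blinding to reduce selection and evaluation bias. With 15 subjects per group and primary outcomes that include examiner-graded hyperaemia, chemosis and staining, an imbalance within a centre would partly mix treatment with that centre's grader if there is more than one centre. The protocol's wording allows several centres but gives no number.

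**Working it through.** **Inputs from the protocol.** Allocation 1:1, balanced by centre (7.1). 15 per group and 30 in total, with 26 as the calculated requirement before losses (6.6.1). Outwardly identical envelopes, one number each, offered for choice (7.3). Lower recruitment than projected is a listed reason for early termination (9.2).

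**Assumptions, because the protocol is silent.** A set of 30 envelopes, 15 per arm; picks are random and envelopes are not put back; block size 4 for the comparison in step 4.

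**Step 1: does list order matter?** Section 7.1 produces a sequence. Section 7.3 removes any outward mark of position and replaces taking the next entry with a choice. No other section restores the order. The list can still fix which product each number stands for. It does not fix which subject meets which number.

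**Step 2: balance under free choice.** The chance that x of m assigned subjects are in one arm is C(15,x) × C(15,m−x) / C(30,m).

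- m = 30: the difference is 0 with certainty. The planned 15:15 is reproduced whatever the picking order.
- m = 26: four envelopes remain, and the arm difference among the 26 equals that among the four. Exact balance: C(15,2)² / C(30,4) = 105² / 27,405 = 11,025 / 27,405 = 0.402. Difference of 4 (a 15:11 split): 2 × C(15,4) / C(30,4) = 2 × 1,365 / 27,405 = 0.0996, about 10%.
- m = 10: 5:5 has probability 3,003² / 30,045,015 = 0.300. A 6:4 split either way has 2 × 5,005 × 1,365 / 30,045,015 = 0.455. Difference of 4 or more: 1 − 0.300 − 0.455 = 0.245.
- m = 8: the same calculation gives 0.215 for a difference of 4 or more.

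**Step 3: other set sizes.** A 5:5 set used up by 10 subjects balances exactly. With 30 subjects drawn from a balanced set of 40, the chance of a difference of 4 or more is 27%. From a set of 60 it is 44%, and 20% for a difference of 6 or more.

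**Step 4: how much is due to the choice?** If the list is one random ordering of 15 and 15, its first m entries are themselves a random draw of m from the set. Using it in order therefore has exactly the distribution in step 2. Simulation of 50,000 such lists agrees: 10.0% at 26 assigned and 24.4% at 10.

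With permuted blocks of 4 used in order, both 26 and 10 assigned end two entries into a block (26 = 6 × 4 + 2; 10 = 2 × 4 + 2). Those two entries fall one in each arm with probability 4/6 = 0.67, and otherwise the difference is 2. It never exceeds 2 at any stopping point; simulation gave exact balance in 66% and 67%. The improvement needs both blocks and ordered use. Numbering an unblocked list would restore verifiability but not balance.

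**The case against.** The best defence is that blind drawing among indistinguishable envelopes is itself a chance mechanism, the sponsor's list still fixes which product each number stands for, and the study is masked and exploratory. Much of this stands, and it rules out several stronger readings.

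- *A reader might infer that the promised balance is not delivered.* The protocol does not show that. An equal-arm set that is used up balances exactly, and the probabilities above need a set that outlasts enrolment. A set of 30 at a centre enrolling 8 or 10 is an assumption, and one that sits awkwardly with the per-centre balance in 7.1.
- *A reader might infer that assignment leaves no trace.* Bottles carry an assignment number (7.4), the centre registers medication delivered (6.3.4.1) and counts it before return (6.3.4.3), and the monitor reviews product accountability (9.1). Who received which number can be reconstructed. Whether that number was the one due cannot.
- *A reader might infer that selection bias is built in.* Selective offering or re-picking steers treatment only if the presenter knows which number means which arm. Envelopes hold numbers and products are masked, and no leak is identified. The risk is reduced but not excluded, because the protocol does not say whether numbers are unique to a subject or shared within an arm.
- *A reader might take it as settled that participants choose.* The translated sentence leaves open who does.

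Calling the arms strata in 7.1 may be only loose terminology. The substantive gap is that the sentence names no balancing mechanism. None of this supplies an order of use, so the central point remains.

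**Conclusion.** The point holds in limited form and is a should-fix. Section 7.3 describes a choice, so the order of the generated sequence does not govern who gets which intervention number, and adherence to that order cannot be checked. The 1:1 balance per centre is not guaranteed when a centre does not use up an equal-arm set, a situation that 9.2 makes foreseeable. Its size, for an assumed 15:15 set and random picks, is about a 10% chance of a difference of 4 or more at 26 assigned and 24.5% at 10. It is nil if the set is exhausted. These probabilities measure free choice and absence of blocking together and cannot be charged to the choice alone. Confounding with a centre's grader would also require several centres, which the protocol permits but does not establish.

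**What to change.** In 7.3, replace the sentence that offers the envelopes for choice with wording such as: *Each centre receives sealed, opaque, consecutively numbered envelopes prepared from its own permuted-block list. Once eligibility is confirmed at the baseline visit, the next envelope in strict order is opened, after the subject number, date and time have been written on it. All envelopes, used and unused, are retained for monitoring.*

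In 7.1, replace "Two strata corresponding to the intervention groups will be used, which will be balanced for a research center" with: *Allocation will use permuted blocks within each research centre; the block size is held by the sponsor and not disclosed to the centre.* It would also help to say whether intervention numbers are unique to each subject.

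The cost is a wording change and numbering envelopes that the sponsor already prepares, with no extra subjects, visits or staff. One limit should be understood: with blocks of 4, for example, the cap of 2 applies within each centre, so small differences at several centres with incomplete blocks can add up in the overall total.

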7.4 Blinding (Masking)

The blinding will correspond to the research subject and the principal investigator. In addition, the statistical analysis will be carried out in a blinded manner for the partial and final analysis.

The masking will be done using boxes in the primary packaging identical in the two groups. Blinding for the research subject and the researcher will be done by replacing the commercial labels in the case of the comparator in the bottles and the use of identical labels that contain the assignment number.

7.4.1 Opening of blinding

Blinding may be opened in the following cases:

1. Presence of a serious adverse event.
2. Safety alarm due to the use of the drugs under study.

3. In case the sponsor determines it for any security reason or other reason that it considers pertinent.

8. Methods Collection, administration and data analysis

8.1 Methods of data collection

A clinical monitor will be assigned to each research center, which will be authorized to monitor, review, procure and ensure that the quality of the information obtained from the participants is reliable and trustworthy. Each monitor will schedule periodic visits to the research centers in order to review the source documents and corroborate the information captured in the case report format (CRF). All clinical monitors will be trained in relation to the information of the study protocol (objective, visits, procedures, range of accepted values, etc.). In the event that the data are not identical between the two registers, the clinical monitor will generate a discrepancy, which must be resolved by the research center in time that the sponsor deems reasonable to meet the objectives of the clinical study. The correction of the discrepancies will be made according to the Good Documentation Practices.

The data registered in the CRF will be reviewed by personnel of Sophia Laboratories, S.A. of C.V trained in the ophthalmological, clinical and pharmacological area, which will have the power to generate discrepancies in the event that the data do not adhere to the stipulations of the research protocol or endanger the participants.

Once all discrepancies generated by the team of clinical monitors and clinical staff have been resolved, the data will be downloaded into an electronic database (Excel Sheet) by personnel designated by the sponsor. A new review of the data will be carried out to corroborate the fidelity of the same and new discrepancies may be generated in case it was considered.

The database generated will be safeguarded by the sponsor and will only have personal access designated by the same.

8.1.1 Strategies to complete the follow-up

- You will be clearly informed of the importance of the study and the benefits that the population will obtain from the results of the study.
- Transportation assistance will be provided in order for the participant to attend their visits.
- In case the IP deems it convenient, it can make calls or send text messages or via email to the research subject. The content of these must be previously approved by the ethics committee.
- A printed calendar will be provided with the objective of reminding the participant of their appointments and the activities that will be carried out, in addition to the estimated duration of the same.
- In case the participant does not attend his / her appointment, the research center must make a call to know the reason and try to arrange a new appointment within the established window period or an unscheduled appointment.
- In case it is not possible to make an appointment, it will be asked about the presence of adverse events and the reason for leaving the study, such as minimum data.

8.2 Data management

The subject's medical record (including clinical notes, test results, etc.), as well as the subject's diary, and the ICO questionnaire are considered source data.

The IP or the designated person of your team will fill out the Case Report Format (CRF) as well as all other documents provided by the sponsor (for example, documents related to the handling of the treatment).

A CRF was designed to record the data that are required in the protocol and that the researcher collects in each of the visits.

In the case of self-assessment questionnaires, it is not permissible for the principal investigator or person responsible for filling in to modify what was written by the subject of the study.

The data capture in the investigator's site will be done by the investigator or the designated person of his team after performing the Medical File. The researcher or a designated person of your team will be trained in the filling of the CRF

All corrections to the CRF data should be made by the investigator or the designated person of your team in accordance with the instructions provided.

To ensure the confidentiality and security of the data, user names and access codes will be used to restrict access to the system only to authorized personnel.

The monitor must ensure that all the data has been filled in the CRF. After comparing the data against the source documents, in case a correction or clarification is necessary, the monitor will request it from the researcher; which must be answered and closed as soon as possible.

The Scientific Committee of Laboratories Sophia, S.A. of C.V. will give the latest medical-scientific review, and will set the standard for freezing the database.

8.3 Statistical methodology

8.3.1 Analysis of primary and secondary outcome variables.

The statistical analysis will be carried out by personnel from Sophia Laboratories, S.A. of C.V The statistical program SPSS version 19 (IBM Corporation, Armonk, NY, USA) will be used.

The designated personnel will be blinded to the intervention groups. The coding will be done using consecutive numbers for each intervention group.

The data will be collected and sorted in an excel sheet. Later they will be exported to the platform of the SPSS program. The variables will be categorized according to their nature.

The result of the continuous quantitative variables will be presented in measures of central tendency: media, standard deviation and ranges. **See Table 6.** Scales to be used

The normal distribution of the results will be obtained by the Kolmogorov-Smirnov test.

The statistical analysis of the continuous **quantitative variables** to find significant differences (p) will be the following:

- Intra-group analysis: Wilcoxon rank test.
- Inter-group analysis: Mann-Whitney U test.

The level of difference to consider significance will be of an alpha of 0.05 or less.

The result of nominal and ordinal qualitative variables will be presented in frequencies, proportions and percentages. See table 1 (section 6.4.3).

The statistical analysis to identify significant differences of the **qualitative variables** will be done by creating 2x2 contingency tables and will be done as follows:

- Intra-group difference: McNemar test.
- Difference between groups: test χ^2 (Chi-square) of Pearson.

The level of difference to consider significance will be of an alpha of 0.05 or less.

For the reporting of adverse events all eyes of those participants who were randomly assigned to an intervention group after the baseline visit will be considered. The results will be expressed in number of cases (eyes).

The final report of the results will be shown in tables or graphs, as appropriate.

It will be considered that the investigational drug is safe and tolerable when there are no clinical and statistical differences in all the variables of primary outcome, with respect to its comparators.

Those subjects who comply with an adherence greater than 60% will be included in the statistical analysis to meet the objective of the study. It was considered that from the minimum dose necessary to obtain a pharmacological effect and the presence of adverse events (exposure) is sufficient to fulfill the general objective of the design, according to the pharmacological characteristics of the product under investigation.

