
Reference product, dose and route of administration, lot:
 
 - Sophixin Ofteno. Ciprofloxacin 0.3% ophthalmic solution. Prepared by Laboratories Sophia, S.A. of C.V., Zapopan, Jalisco, Mexico. - Dosage: 1 drop every 2 hours during the waking period (8 daily applications), on day 1 and 2; continuing with 1 drop every 4 hours during the waking period (4 daily applications) from day 3 to 7. Both eyes. - Route of administration: ophthalmic

Evaluation criteria:
 
Primary security outcome variables:
 
 - Presence of adverse events. - Intraocular pressure. - Visual ability - Laboratory tests: BHc, QS and PFH. - Ocular surface staining with fluorescein and lissamine green using Oxford scale - Ophthalmological signs: conjunctival hyperemia, chemosis. 
Primary outcome variables of tolerability:
 
 - Burning - Foreign body sensation - Itching - Eye comfort index 
Primary outcome variables of tolerability:
 
 - Burning - Foreign body sensation - Itching - Eye comfort index

Statistical methodology:
 
The data will be expressed with measures of central tendency: mean and standard deviation for the quantitative variables. The qualitative variables will be presented in frequencies and percentages. The statistical analysis will be carried out through the Mann-Whitney U test for quantitative variables for the difference between the groups. The intra-group difference will be made with the Wilcoxon rank test. The difference between the qualitative variables will be analyzed by means of X² (Chi²). An alpha ≤ 0.05 will be considered significant.

2. Content

1. SUMMARY	1
2. CONTENT	3
3. INDEX OF ABBREVIATIONS	7
4. ADMINISTRATIVE STRUCTURE OF THE STUDY	9
5. INTRODUCTION	11
5.1 THEORETICAL FRAMEWORK	11
5.2 DEFINITION OF THE PROBLEM AND FUNDAMENTAL REASON	12
5.3 BACKGROUND	12
5.3.1 LEVOFLOXACINO	12
5.3.1.1 Pharmacodynamic properties	13
5.3.1.2 Pharmacokinetics in ophthalmic application	14
5.3.1.3 Clinical efficacy	14
5.3.1.4 Security	16
5.4 JUSTIFICATION	16
5.5 OBJECTIVES AND HYPOTHESIS	16
5.5.1 GENERAL OBJECTIVE	16
5.5.2 SPECIFIC OBJECTIVES	16
5.5.3 HYPOTHESIS	17
5.6 STUDY DESIGN AND PLAN	17
5.6.1 DISCUSSION OF THE STUDY DESIGN	18
6. MATERIAL AND METHODS. PARTICIPANTS, INTERVENTIONS AND VARIABLES	18
6.1 STUDY CENTER	18
6.1.1 ORGANIZATION OF THE CENTER	18
6.1.2 DOCUMENTATION TO BE DELIVERED TO SPONSOR	19

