5.5.2 Specific objectives

- Describe the safety of the PRO-174 ophthalmic solution through the presentation of adverse events.

- Describe the safety of the PRO-174 ophthalmic solution through changes in intraocular pressure.
- Describe the safety of the ophthalmic solution PRO-174 by means of changes in visual capacity.
- Describe the safety of the PRO-174 ophthalmic solution through changes in laboratory tests.
- Describe the safety of the ophthalmic solution PRO-174 through changes in ocular surface stains.
- Describe the safety of the ophthalmic solution PRO-174 through changes in ophthalmological signs (conjunctival hyperemia and chemosis).
- Describe the safety of the ophthalmic solution PRO-174 by means of changes in the time of tear rupture.
- Describe the safety of the PRO-174 ophthalmic solution through changes in vital signs.
- Describe the safety of the ophthalmic solution PRO-174 by means of changes in the posterior segment.
- Describe the tolerability of the ophthalmic solution PRO-174 through the presence of ocular symptoms (burning, foreign body sensation and pruritus).
- Describe the tolerability of the ophthalmic solution PRO-174 through changes in the ocular comfort index.
- Describe the safety of the Sophixín Ofteno® ophthalmic solution through the presentation of adverse events.
- Describe the safety of the Sophixin Ofteno® ophthalmic solution through changes in intraocular pressure.
- Describe the safety of the Sophixín Ofteno® ophthalmic solution through changes in visual ability.
- Describe the safety of the Sophixin Ofteno® ophthalmic solution through changes in laboratory tests.
- Describe the safety of the Sophixin Ofteno® ophthalmic solution through changes in ocular surface stains.
- Describe the safety of the Sophixín Ofteno® ophthalmic solution through changes in ophthalmological signs (conjunctival hyperemia and chemosis).
- Describe the safety of the Sophixin Ofteno® ophthalmic solution by means of changes in the tear rupture time.
- Describe the safety of the Sophixín Ofteno® ophthalmic solution through changes in vital signs.
- Describe the safety of the Sophixín Ofteno® ophthalmic solution through changes in the posterior segment.
- Describe the tolerability of the ophthalmic solution Sophixín Ofteno® by means of the presence of ocular symptoms (burning, sensation of foreign body and pruritus)
- Describe the tolerability of the ophthalmic solution Sophixín Ofteno® by means of changes in the ocular comfort index.

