8.3.2 Additional analyzes

No additional analyzes are contemplated to those previously described. Nevertheless, these may be performed in the event that during the conduction of the study it is required to analyze specific safety aspects of any intervention, maintaining the blinding until the end of the study..

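### For the quantitative primary measures, the between-arm test has no defined input and no baseline adjustment, so it is valid but less precise than the collected data allow

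*Combined protocol and SAP*

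**What the plan says.** The Summary states: "The statistical analysis will be carried out through the Mann-Whitney U test for quantitative variables for the difference between the groups". Section 8.3.1 repeats this for continuous quantitative variables as "Inter-group analysis: Mann-Whitney U test". Neither place says what enters the test: the final-visit value, the value at each visit, or the change from baseline.

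Baseline has a natural role only within an arm, through "Intra-group analysis: Wilcoxon rank test" and McNemar for qualitative variables. Section 8.3.2 adds: "No additional analyzes are contemplated to those previously described".

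Most specific objectives in section 5.5.2 are worded as changes, for example "Describe the safety of the PRO-174 ophthalmic solution through changes in intraocular pressure" and "Describe the tolerability of the ophthalmic solution PRO-174 through changes in the ocular comfort index". Adverse events are not: "Describe the safety of the PRO-174 ophthalmic solution through the presentation of adverse events". Burning, foreign body sensation and itching are described by their presence.

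The timeline table schedules intraocular pressure and ocular surface integrity at screening, baseline, visit 1 and the final visit. The comfort index is taken at baseline and the final visit, and laboratory samples at screening and the final visit. The footnote to that table lets screening values up to 10 days old stand in for baseline. The baseline-visit text in section 6.5.1 allows 7 days.

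**The concern.** The plan collects a pre-treatment value for each quantitative primary measure but does not specify its use when the arms are compared. This leaves two problems.

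First, the tested quantity is open. Final values and change scores can give different answers in the same data, and nothing fixes the choice in advance.

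Second, neither choice is efficient in all circumstances. Final values leave in the between-subject variation that baseline could explain. Change scores remove it fully only when the correlation is high, and add noise when it is below 0.5.

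Precision matters in this trial because section 8.3.1 calls the drug safe and tolerable when no clinical and statistical differences are found in the primary variables. Under that rule a less precise comparison makes the favourable conclusion easier to reach.

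**Working it through.** **The plan's own figure.** The protocol gives no power or detectable difference for any quantitative variable. Its only sample-size result (section 6.6.1) concerns adverse-event proportions: 12.5, rounded to 13 per group. Reading the two rates as 0.073 and 0.60 (the second is not stated as a rate), the pooled two-proportion formula gives

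[1.96 × √(2 × 0.3365 × 0.6635) + 0.84 × √(0.073 × 0.927 + 0.60 × 0.40)]² / 0.527² = (1.310 + 0.466)² / 0.2777 = 11.4, or 12 per group.

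That is close to 13, but only on this reading. Nothing below depends on it.

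**Which variables are affected (Table 6).**
- Continuous: intraocular pressure and most laboratory values.
- Discrete: comfort index, staining grade and the white-cell differential percentages. They reach the Mann-Whitney test if analysed as quantitative.
- Nominal or ordinal: visual ability, chemosis, burning, foreign body sensation, itching (nominal) and hyperemia (ordinal). They fall under the rule that begins "The difference between the qualitative variables will be analyzed by means of" and go to chi-square.
- Adverse events have no baseline value that could serve as a covariate.

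**Inputs.** From the documents: 15 subjects per group and 1:1 allocation, alpha 0.05, z = 1.96 and 0.84 (sections 6.6.1, 7.1 and 8.3.1). Assumed: a true difference of 1 SD, a baseline-final correlation ρ of 0.3 to 0.8, normal data, and the subject as the unit. The plan counts 60 eyes; that is a separate matter.

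**Formulas.** Relative to the variance of the final value, the variance is 1 for final values, 2(1 − ρ) for change and 1 − ρ² after baseline adjustment. On final values, the difference detectable with 80% power is (1.96 + 0.84) × √(2/15) = 2.80 × 0.365 = 1.02 SD. The other columns multiply this by the square root of the relative variance.

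| ρ | Variance, change | Variance, adjusted | Detectable, final | Detectable, change | Detectable, adjusted |
|---|---|---|---|---|---|
| 0.3 | 1.40 | 0.91 | 1.02 SD | 1.21 SD | 0.98 SD |
| 0.5 | 1.00 | 0.75 | 1.02 SD | 1.02 SD | 0.89 SD |
| 0.7 | 0.60 | 0.51 | 1.02 SD | 0.79 SD | 0.73 SD |
| 0.8 | 0.40 | 0.36 | 1.02 SD | 0.65 SD | 0.61 SD |

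**Simulation.** Power from 4,000 normal trials per cell, 15 per arm, 1 SD difference:

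| ρ | Mann-Whitney, final | Mann-Whitney, change | ANCOVA | Rank ANCOVA |
|---|---|---|---|---|
| 0.3 | 71-72% | 57% | 77% | 75% |
| 0.5 | 71-72% | 71% | 84% | 82% |
| 0.7 | 71-72% | 90% | 95% | 92% |
| 0.8 | 71-72% | 98% | 99% | 97% |

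With no true difference, rejection rates were about 4-5% for every method. The mean 95% CI width fell from 1.48 SD unadjusted to 1.44 / 1.31 / 1.08 SD with ANCOVA at ρ = 0.3 / 0.5 / 0.7. About 2 to 3 points of ANCOVA's advantage come from the data being normal rather than from the baseline. This shows in the gap between the last two columns, and at ρ = 0, where ANCOVA reaches about 74% against 72% for Mann-Whitney.

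**The case against.** The strongest defence is that an unadjusted rank test is valid after randomisation, and that in a 30-subject trial labelled exploratory adjustment is a matter of efficiency. The validity part stands. A reader might infer that chance baseline imbalance makes the planned test produce too many false positives. It does not: its error rate stays at about 4-5% at every correlation, and adjustment would not lower it.

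A reader might also infer that the plan ignores baseline. The text is silent on the tested value, and Mann-Whitney on change from baseline is compatible with it. At ρ of 0.7 to 0.8 that choice would lose almost nothing against rank ANCOVA (90% against 92%, and 98% against 97%). This does not rescue the plan, because the choice is not fixed, and at ρ = 0.3 the change score is the worst option, at 57%.

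A third tempting reading is that every primary measure is affected. Table 6 and the nature of adverse events rule that out.

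A fourth is that the objectives demand a between-arm comparison of changes. Each specific objective names one product and asks for a description, which the within-arm tests can answer. The wording shows that change is of interest but does not prescribe the between-arm test.

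The size of the gain is also open to challenge. The documents give neither the difference nor the correlation. The entry limits (intraocular pressure 11 to 21 mmHg, laboratory values within normal limits with a 10% margin) restrict the baseline range, which tends to lower the correlation and hence the gain. Finally, adjustment leaves the rule of inferring safety from the absence of a difference intact. These points limit the size of the finding; they do not remove it.

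**Conclusion.** The point holds for intraocular pressure, laboratory values and, if analysed as quantitative, comfort index and staining grade. The plan leaves the tested value undefined and specifies no baseline-adjusted comparison, although the data for one are collected.

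Against final values, ANCOVA gains about 5 points of power at ρ = 0.3 and about 23 at ρ = 0.7. Against change scores it gains 20 points at ρ = 0.3 and 1 at ρ = 0.8. No single unadjusted choice does well across the range, whereas adjustment is at or near the best throughout. These sizes rest on the assumed 1 SD difference, the assumed correlations, normal data and 15 analysed subjects per arm. The direction does not, apart from a negligible small-sample cost if the correlation is near zero.

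This is an improvement the sponsor should make, not a flaw that invalidates the test. It carries weight because lost precision works in favour of the conclusion that the drug is safe and tolerable.

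**What to change.** In section 8.3.1, state that for each quantitative primary variable the arms are compared at the final visit with ANCOVA of the final value on treatment and its own baseline. Use one value per subject: the mean of both eyes for intraocular pressure and staining, and the single value for laboratory tests and comfort index. Report the adjusted difference with its 95% CI.

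Keep Mann-Whitney, with its input defined, or a pre-specified rank ANCOVA, as the sensitivity analysis for skewed variables. Name it in advance so that the choice does not follow the data. Rank ANCOVA gives no difference in measurement units, so the reported estimate should come from the main model.

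Define baseline as well. The 10-day allowance in the timeline footnote and the 7-day allowance in the baseline-visit text must be reconciled.

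Adverse events and the variables classed as nominal or ordinal stay outside this change. The cost is a short paragraph of plan text and a standard SPSS procedure. No new measurements or subjects are needed.
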